### **Study Design**

**Overview.** This parallel arm, individually randomized control trial (RCT) will recruit 34 older adults from Dallas and neighboring counties. We aim to retain at least 30 participants on whom immediate post-training gains in both *near* and *far* abilities can be observed. This RCT shall be registered at [ClinicalTrials.gov](https://clinicaltrials.gov). There will be a Clinical Coordination Team (co-directed by [name] and the Project Manager) that will implement the intervention and check in with the participants on a weekly basis regarding their training progress. A blinded data collection team, directed by a post-doctoral fellow, will collect both behavioral and neuroimaging assessments before and after training. There will also be

a Data Coordination Team (co-directed by [name] and a post-doctoral fellow) that will be responsible for scoring and preprocessing the data. All data will be deposited in a HIPAA compliant server at the PI's laboratory. The team leaders will meet twice a month and each team will meet weekly to oversee any issues with subject recruitment, logistics and data collection. We will also recruit a total of 20 younger adults (YA, 18-30 years of age) for neuroimaging, who will be the functional controls for the older adults in the RCT.

This is a Phase 1 trial with multiple interventions in older adults, where the goal is to compare high attentional control trainings (High-C and High-C+) to low attentional control training (Low-C) and evaluate training-related changes in neurocognitive functions of both near (secondary outcome) and far transfer (primary outcome) tasks.

***Experimental Design.*** There are three intervention arms for older adults (OA) in this RCT trial, where attentional control demands in working memory training will be systematically increased using engaging game-based simulations.

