***Sample Size Justification for the older adults in the RCT.*** We estimated the power (using G\*power3.1) to detect the differences between the Training Arm (3) x Assessment (2) interaction on the primary cognitive outcome. *The current study is the first phase of a larger randomized controlled trial. We calculate our power for the full trial, but our requested sample size for this study is 51.* We will recruit 177 older adults with the aim to retain a total sample size of 144 older adults at immediate post-training with the expected attrition of 18%. We report two expected effect sizes of Cohen's *f* for our calculations. One,  $f=.35$ , the minimum effect size obtained across our 3 pilot studies. Another,  $f=.16$ , based on a meta-analysis on computer-based cognitive training in older adults. The proposed total sample size of 144 older adults will provide us with >93% power to detect the Training Arm (3: Low-C, High-C, High-C+) x Assessment

(A vs. B) interaction at  $f=.16$  and  $>98\%$  power to detect the interaction at  $f=.35$  on the primary cognitive outcome at  $p<.05$ . It will also provide  $>90\%$  power to detect a meaningful between-group difference ( $f=.35$ ) at immediate post-testing, after controlling for baseline cognition, at  $p<.05$ . At +6mo retention period (Assessment C), we expect to retain a total of 117 older adults, after the expected  $\sim 20\%$  attrition between Assessments B and C. This will provide us with  $>87\%$  power to detect the Training Arm (3: Low-C, High-C, High-C+) x Assessment (2: A vs. C) interaction at  $p<.05$  at  $f=.16$ . We will conduct 2 ANOVAs, one for primary and one for secondary. Our proposed sample size will provide us with sufficient power ( $>87\%$ ) to detect the Training Arm (3) x Assessment (2) interaction at a corrected  $p$  value of .025 ( $=.05/2$  for 2 cognitive outcomes of interest).

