***Analyses of Primary and Secondary Neuroimaging Outcomes.*** There are two main fMRI tasks of interest- one for primary cognitive outcome (episodic memory), called *subsequent memory*; another for secondary cognitive outcome (executive control), called *task-switching*. An additional fMRI task, *working memory updating*, a near transfer task for all arms, will also be evaluated. For each task, we will derive a summary BOLD measure that best characterizes neural activity for the task after correcting for multiple comparisons. Those summary values will be entered into an ANOVA, where the Training Arm (3: Low-C, High-C, High-C+) x Assessment (pre-test vs. post-test) interaction will be evaluated, followed by post-hoc analyses of these interaction effects. We will also calculate group differences in the contrasts of interest at the post-test scans. The critical contrasts of interest for the subsequent memory is Remembered vs. Forgotten items, and for task-switching is Dual vs. Single task. The resulting ROI clusters, after correcting for multiple comparisons, will be used to extract percent signal change for all individuals at both pre-test and post-test. Specific Aim 2 evaluates whether the post-training changes in fronto-parietal activations are largest in the High-C and High-C+, compared to the Low-C, training arms. The percent signal change data will be submitted to a Training Arm x Assessment ANOVA, which will be followed by planned-comparisons between the groups to evaluate the specific aim 2. These interaction effects will be conducted for all task difficulty conditions in the fMRI tasks, because post-intervention activation patterns are hypothesized to be different for simpler conditions (e.g., 0-back; Single task; water present) compared to the more difficult conditions (e.g., 3- back, Dual task; water absent) of the fMRI tasks. We will also calculate task-specific activations for difficult vs. simpler condition contrasts (e.g., 3-back>0-back; Dual>Single; water absent>water present) in younger adults (YA), after correcting for multiple comparisons. The resulting ROI

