clusters from YA will be used to extract percent signal change for all older individuals (OA) at both assessments. A univariate ANOVA with 3 groups (post-test Low-C, post-test High-C+, and YA) will be conducted to evaluate whether the post-test activations in High-C+ older adults in these task-related regions are closest to that of YA. We predict that for the primary (subsequent memory) and secondary (task-switching) outcomes, High-C and High-C+ older adults at post-training will have increased task-related neural activations mimicking that of younger adults, and reduced non-compensatory over-activations compared to baseline.

For the network analyses, we will utilize seed-to-voxel based connectivity from the major nodes within two cognitive networks, Fronto-Parietal (FP) and Cingulo-Opercular (CO), at both pre- and post-testing sessions. Changes in post-training functional connectivity in these two networks will be evaluated at all task difficulty conditions for memory updating (0-back, 3-back), task switching (single task, dual task), and subsequent memory task (water present, water absent). The interaction effects will help evaluate whether the connectivity of attentional networks change most for the higher attentional control training groups. We will also conduct separate pair-wise comparisons between High-C and High-C+ for both primary (*Subsequent Memory*) and secondary (*Task Switching*) cognitive outcomes, corrected for multiple comparisons, to determine if High-C+ engenders most neural changes.

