## Outcome Measures

### *Name:*

1. Episodic Memory: Cognitive
2. Episodic Memory: fMRI
3. Executive Functions: Cognitive
4. Executive Functions: fMRI
5. Reasoning
6. Working Memory Capacity
7. Psychosocial Well-being
8. Diffusion Tensor Imaging

**Primary Outcome:** Episodic Memory: Cognitive; Episodic Memory: fMRI

**Secondary Outcome:** Executive Functions: Cognitive; Executive Functions: fMRI

**Other:** Reasoning, Working Memory Capacity, Psychosocial Well-being, Diffusion Tensor Imaging

**Time Frame.** All behavioral and cognitive measures (episodic memory, Executive functions, reasoning, working memory and psycho-social well-being) will be collected at the following three time points: Baseline (Assessment A), Immediate Post-training (Assessment B), and Retention (Assessment C).

Neuroimaging measures, including DTI and the fMRI tasks of episodic memory and executive functions will be collected at only two time points: Baseline (Assessment A) and Immediate Post-training (Assessment B).

Episodic memory (Cognitive) will be characterized by a single score that will be obtained by averaging standardized scores of 4 episodic memory tasks, including a task of everyday memory. These tasks are *Picture Sequence Memory task* (from NIH toolbox), *Buschke's Selective Reminding Test*, *Story Recall* (from expanded MMSE) and *Rivermead Behavioral Memory Test* (a test of everyday memory).

Episodic memory (fMRI) will be characterized by BOLD activations in an event related *subsequent memory* fMRI task. Scanning will take place during encoding of 96 color photographs of outdoor scenes (4 s duration) interspersed with baseline trials of a fixation cross (of 4-16 s). During encoding, the participant will determine if water is present in the scene with a keypress. Twenty minutes after the scan, the participant will undergo a recognition judgement task along with confidence ratings of their responses, assessing their subsequent memory of scenes presented in the scanner. In this episodic memory task, the following contrasts will be assessed for each subject for both "water present"

(easy condition) and “water absent” (hard condition) scenes: Forgotten>Remembered items and Remembered>Forgotten items.

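### As written, the regions for the Specific Aim 2 fMRI test are chosen from post-test arm differences and then tested for Training Arm x Assessment on the same participants, which biases p-values and effect sizes in those regions

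*Combined protocol and SAP*

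**What the plan says.** The relevant text is the paragraph on neuroimaging outcomes in the Data Analysis Plan. It first describes a summary BOLD measure for each task, entered into a Training Arm x Assessment ANOVA. It then adds a second line of analysis, in this order:

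1. "We will also calculate group differences in the contrasts of interest at the post-test scans".
2. A sentence naming the contrasts: Remembered vs Forgotten for subsequent memory, Dual vs Single for task-switching.
3. "The resulting ROI clusters, after correcting for multiple comparisons, will be used to extract percent signal change for all individuals", at both pre-test and post-test.
4. A statement of Specific Aim 2, then "The percent signal change data will be submitted to a Training Arm x Assessment ANOVA", followed by planned comparisons between groups. The interactions are to be examined for every difficulty condition.

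The same section later defines regions in the younger adults: "clusters from YA will be used to extract percent signal change for all older individuals (OA) at both assessments". The only test named on those regions is a three-group post-test comparison that includes the younger adults.

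Outcome Measures lists the primary outcome as "Episodic Memory: Cognitive; Episodic Memory: fMRI".

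**The concern.** The only group-level result to which the resulting clusters in step 3 naturally refer is the arm comparison at post-test in step 1. No split sample, cross-validation, atlas definition or arm-pooled selection is stated for this ANOVA.

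The interaction in step 4 compares post-test minus pre-test between arms, so it reuses the post-test values that caused the region to be chosen. Where the arms differ at post-test by chance, part of that chance difference carries into the change score. The correction for multiple comparisons limits how many regions are selected. It does not restore the null distribution of a second test inside them.

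At stake is the evidence for Specific Aim 2, which the plan ties to the percent-signal-change ANOVA. The plan calls this study the first phase of a larger trial, so inflated effect sizes could also be carried forward.

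**Working it through.** **The plan's own figure.** The documents give no power or error rate for the region-level fMRI test. The nearest figure is for the same interaction on the cognitive outcome: "The proposed total sample size of 144 older adults will provide us with >93% power to detect the Training Arm" by Assessment interaction at f=.16. With lambda = f²·N·m/(1-rho), m=2 assessments and rho=.5 (assumed), lambda = .0256 x 144 x 2/.5 = 14.75. With 2 and 141 degrees of freedom, power is .935, so the figure reproduces.

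**Inputs for the check.**
- Three arms and two assessments, from the Data Analysis Plan.
- 30 retained, from Study Design ("We aim to retain at least 30 participants on whom immediate post-training gains"). This is 30/3 = 10 per arm if allocation is equal (assumed).
- The full trial, from the sample size section: "We will recruit 177 older adults with the aim to retain a total sample size of 144 older adults at immediate post-training". This is 144/3 = 48 per arm.
- Test level .05, assumed because none is stated for the region-level ANOVAs.
- Pre-post correlation rho of .3, .5 and .7, and selection at p<.001 per location. Both are assumed; the documents give neither.

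**Selection and test are not orthogonal.** With equal variances, post-test and change correlate at sqrt((1-rho)/2):
- rho=.3: sqrt(.35) = .59
- rho=.5: sqrt(.25) = .50
- rho=.7: sqrt(.15) = .39

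A valid selection rule would give zero.

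**Null simulation, selecting contrast retested.** No arm effect. Locations are selected on the post-test one-way F, then the one-way F on change is tested at .05.

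| Setting | rho .3 | rho .5 | rho .7 |
|---|---|---|---|
| 10 per arm, selection p<.001 | 44% | 30% | 20% |
| 10 per arm, selection p<.01 | 32% | 23% | 15% |
| 48 per arm, selection p<.001 | 49% | 35% | 23% |
| Regions from the mean over all arms and both sessions (10 per arm) | 5.1% | 5.4% | 5.0% |

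Separate runs of the first row agree within about 3 percentage points (41-44%, 30-31%, 18-20%). The full-trial sample size does not cure the problem.

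**Effect size.** With 10 per arm, rho=.5 and selection at p<.001, mean eta-squared for the interaction under the null is .16 in selected locations against .07 in unselected ones. As f on the change score, this is .42 against .25. That scale should not be set beside the f values of .16 and .35 in the power section, which concern the cognitive outcome.

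**Single conditions tested.** The plan selects on a contrast (for example Dual vs Single) but also tests each condition. If between-condition correlation r and pre-post correlation act separately, the selecting contrast at post-test and the change in one condition correlate at sqrt((1-r)/2) x sqrt((1-rho)/2). This is .59 x .59 = .35 at r=rho=.3, and .39 x .39 = .15 at r=rho=.7. The overlap is weaker, and simulated conditional error is about 7-18% (r of .3 to .7 assumed).

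**With cluster correction.** Smooth 3D null fields were used with 10 per arm, cluster-forming p<.001, cluster size calibrated to 5% familywise error, and the largest surviving cluster tested:
- rho=.5: 116 of 2,351 runs survived; the ANOVA was significant in 51% of them (standard error sqrt(.51 x .49/116) = about 5 points).
- rho=.7: 117 of 2,406 runs survived; significant in 31%.

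Correction therefore leaves the conditional bias in place. The joint chance of a surviving cluster and a significant ANOVA at rho=.5 is .05 x .51 = about 2.5% per contrast.

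**The case against.** The best defence is that the text is ambiguous. The sentence naming the task contrasts stands between the post-test arm comparison and the clusters. For the younger adults, similar wording plainly means task-contrast clusters. If the older-adult clusters came from the task contrast pooled over arms, the interaction test would run at about 5%. This has weight: the sponsor may have intended it. But the text does not say so, and sentence order points the other way.

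The plan also has regions from younger adults, extracted in older adults at both assessments. That helps, but the Aim 2 interaction is not assigned to them.

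Three stronger readings are tempting, and the documents do not support them:

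- A reader might infer that the fMRI primary outcome as a whole rests on a circular test. The plan also has a Training Arm x Assessment ANOVA on a task-level summary BOLD measure, and nothing shows that this measure is selected on arm.
- A reader might infer a study-level false-positive rate of 20-44%. Those rates are conditional on a region having been selected; with real familywise control the joint rate is about 2.5% per contrast.
- A reader might infer that a spurious interaction is generally likely once a region is selected. The location-level rates stay below one half, the condition-level rates are lower still, and only the cluster-averaged case at correlation .5 reaches about one half.

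**Conclusion.** The concern holds for the percent-signal-change ANOVA under Specific Aim 2, on the natural reading of the paragraph. Region selection and test share the post-test data, so p-values and effect sizes in the selected regions lean towards a training effect. Conditional on selection, the nominal 5% test runs at about 20-44% when the selecting contrast is retested and about 7-18% for single conditions.

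The size rests on assumed pre-post and between-condition correlations of .3 to .7, selection at p<.001, equal arms of 10 and a .05 test level. The direction does not depend on the exact values: the correlation between selection and test is above zero whenever pre-post correlation is below 1. The main harm is region-level results that cannot serve as independent evidence for Aim 2, rather than a large rise in the overall chance of a false claim.

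**What to change.** State in the SAP that regions for the Aim 2 ANOVA are defined without arm information, and name one source:

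- the task contrast pooled over all older adults and both sessions;
- the younger-adult clusters already extracted at both assessments; or
- fronto-parietal regions fixed in advance.

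Report regions found from post-test arm differences descriptively only, without an interaction p-value or effect size offered as evidence for Aim 2. If pooled task-contrast clusters were intended all along, one sentence saying so settles the point.

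The cost is SAP wording; data and software are unchanged. The small downside is that regions engaged in only one arm after training may be missed. Pooling both sessions is preferable to baseline alone, because baseline-only regions could miss activation that appears only after training, which the synopsis expects. Younger-adult clusters suit comparisons among the older arms, but the younger adults' own values in them are affected by selection, which should be noted for the three-group comparison.

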Additionally, a single-session, baseline functional neuroimaging data-set will be collected in a control group of 18 younger adults. These younger adults will not undergo any training. High attentional control training arms (High-C and High-C+) are also expected to heighten compensatory brain activation in older adults after intervention, for both episodic memory (primary outcome) and executive control (secondary outcome) in-scanner tasks, paralleling the baseline activity of younger brains. These high attentional control training arms are also expected to positively impact brain structures that progressively decline with aging. The data from younger adults, our functional control group, will provide critical information about the brain regions activated in young, healthy brains during episodic memory (far transfer) and executive functions (near transfer). It will also help us determine whether older adults' brain activity following training resembles that of younger brains.

The primary objectives of this double-blind RCT are to evaluate the efficacy of high attentional control training on episodic memory (primary cognitive outcome) in an older adult population, by evaluating a) immediate training-related

changes in performance and neural activation during episodic memory tasks, and b) long-term changes at a +6-month retention period in performance during episodic memory tasks. The secondary objective of this RCT is to evaluate the efficacy of high attentional control training on executive functions (secondary cognitive outcome) in an older adult population by evaluating neuro-cognitive changes in executive functions immediately after the training, and cognitive gains at +6-month retention period.

In order to achieve these objectives, cognitive measures of both primary and secondary outcomes will be collected in healthy older adults at before training (baseline), immediately after 8 weeks of training (immediate post-training), and 6 months after training completion. MRI scanning, including fMRI tasks of episodic memory (primary outcome) and executive functions (secondary outcome), will be conducted at baseline and at immediate post-training for older adults, and only once in younger adults.

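### The younger-adult fMRI comparison leaves out High-C, and appears to test younger adults in regions chosen from their own scans

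*Combined protocol and SAP*

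**What the plan says.** In the Data Analysis Plan (Analyses of Primary and Secondary Neuroimaging Outcomes), difficult-versus-simpler contrasts are computed in YA. The examples are 3-back>0-back, Dual>Single and water absent>water present. The resulting "clusters from YA will be used to extract percent signal change for all older individuals (OA) at both assessments". Then "A univariate ANOVA with 3 groups (post-test Low-C, post-test High-C+, and YA) will be conducted", to see whether High-C+ is the arm nearest to YA in those regions.

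The next sentence predicts that "High-C and High-C+ older adults at post-training will have increased task-related neural activations mimicking that of younger adults". The Brief Summary makes the same prediction for both arms: "High attentional control training arms (High-C and High-C+) are also expected to heighten compensatory brain activation in older adults after intervention", "paralleling the baseline activity of younger brains". It also gives as one purpose of the YA group to learn whether older adults' "brain activity following training resembles that of younger brains".

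YA contribute one scan each: "a single-session, baseline functional neuroimaging data-set will be collected in a control group of 18 younger adults". The YA number is 18 there, 25 in the Study timeline for Year 1 and 20 in the Study Design overview.

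**The concern.** There are two separate problems.

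**Missing arm.** The ANOVA is meant to show which arm is nearest to YA, but one of the three arms is not in it. If High-C were nearest, this analysis could not show it.

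**Region selection.** A region that passes a threshold in YA does so partly because of chance in those YA scans. If the same scans then supply the YA values, that chance is counted as YA activation. The older arms carry no such excess, so an apparent age gap can arise where none exists. Correcting for multiple comparisons limits the number of false regions. It does not remove the excess in the regions that pass. At stake is the size of the YA-minus-older gap, which is how resemblance would be judged.

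**Working it through.** **1. High-C against the plan's analyses**

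- Training Arm x Assessment ANOVAs: all three older arms, no YA.
- Pairwise High-C versus High-C+ (with the network analyses): no YA.
- Three-group ANOVA: YA, Low-C and High-C+, no High-C.

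No described analysis contains both High-C and YA. A High-C versus High-C+ difference does not replace it, because closeness to YA depends on the YA level.

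**2. Precision of a four-group comparison**

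Inputs: YA n=20 (Study Design) and 30 older adults retained, so 10 per arm if allocation is equal (assumed). Error df = 50 − 4 = 46, t = 2.013.

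Half-width = t × √(1/20 + 1/10) = 2.013 × 0.387 = 0.78 SD of the region mean.

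The biases below are in single-parcel SD. In the parcel model the region-mean SD is about 0.81, 0.62 and 0.57 parcel SD, so in those units the half-width is 0.78 × 0.81 = 0.63, 0.78 × 0.62 = 0.48 and 0.78 × 0.57 = 0.44.

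**3. Size of the selection bias**

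The plan gives no effect size, alpha or power for this comparison, so there is no figure to reproduce. Everything in this step is simulated under assumptions.

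Parcel model: 200 parcels, 50 active, between-parcel correlation .3; no true age difference; 10 per older arm; assumed true contrast 0.5, 0.8 or 1.0 SD. A parcel is selected in YA if its positive t passes the two-sided Bonferroni limit (.05/200). At n=20 that limit is t = 4.49, so the observed mean must reach 4.49/√20 = 1.00 sample SD. When the true value is 0.5, parcels that pass are mostly overestimates.

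Results, in the order 0.5, 0.8, 1.0 SD, with the selecting contrast as outcome:

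| YA n | Region found | ANOVA p<.05, given a region | ANOVA p<.05, all data sets | Smooth-field cluster model |
|---|---|---|---|---|
| 18 | 52, 96, 100% | 36, 18, 10% | 19, 18, 10% | 31, 8, 6% |
| 20 | 62, 98, 100% | 31, 16, 7% | 19, 16, 7% | 27, 8, 5% |
| 25 | 77, 100, 100% | 26, 9, 5% | 20, 9, 5% | 22, 5, 5% |

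The all-data column counts data sets with no region as non-rejections. At n=20: 0.62 × 31% = 19%, 0.98 × 16% = 16%, 1.00 × 7% = 7%.

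False YA excess on the contrast at n=20: +0.38, +0.21, +0.12 SD.

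**4. Which signals carry the bias**

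The difficult and simple conditions each have SD 1 and correlation .5, so the contrast variance is 1 + 1 − 2(.5) = 1. The covariance of the difficult condition with the contrast is 1 − .5 = .5, and that of the simple condition is −.5. Half the bias therefore passes to each condition, with opposite signs. Simulated values agree: difficult +0.19, +0.10, +0.05 SD; simple −0.19, −0.10, −0.06 SD; 6–11% rejections. A signal independent of the selecting contrast is within 0.01 SD of zero, with 5–6% rejections.

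Applied to the tasks:

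- Task-switching: Dual>Single is both the selecting and the critical contrast, so YA would be biased upward on it and on Dual>Fix, and downward on Single>Fix.
- n-back: the same structure.
- Subsequent memory: the selecting example is water absent>water present and the critical contrast is Remembered versus Forgotten. If the latter is tested, it is about unbiased.

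Low-C versus High-C+ rejects in 4–6%, because both arms use the same regions and neither chose them.

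**5. A different model**

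With 500 voxels, one-sided p<.001, true contrasts of 0.3 to 0.8 SD and correlation .2 or .5, the YA excess at n=20 is 0.11 to 0.42 SD, with 6–67% rejections. With regions from an independent YA sample, over YA n of 18, 20 and 25, the bias is −0.02 to +0.01 SD, with 3–8% rejections. The direction agrees; the size varies widely.

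**The case against.** Use of the same YA scans is inferred. The extraction sentence names only older adults, and the signal entered in the ANOVA is not stated. This stands: the second part is conditional, and its firm content is that the plan must state both.

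The size is also uncertain. The largest rates come from the weakest assumed activation, where a region is often not found at all. At 0.8 to 1.0 SD the cluster model is close to nominal. No document figure favours one value. This stands too.

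A reader might infer that the primary fMRI outcome or the main trial tests are invalid. The documents do not support that: Remembered versus Forgotten is not the selecting contrast, and the Training Arm x Assessment test does not use YA as a group.

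A reader might also infer that the bias will name the wrong arm as closest. If both older arms lie below YA, the order is largely kept. With true gaps of −0.50 and −0.20 SD at n=20, the nearer arm is identified in 78%, 86% and 88% of data sets, against 86%, 86% and 85% with fixed regions. The order is at risk when an arm reaches or exceeds YA, which the plan does not predict. Its phrase "reduced non-compensatory over-activations compared to baseline" refers to baseline, not to YA.

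On the missing arm, High-C does appear in other neuroimaging analyses, so it is not left out of the imaging plan. But none of those analyses includes YA. The expectation that frailer adults benefit most from High-C is a cognitive prediction and weak evidence about mean activation; the omission does not depend on it.

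**Conclusion.** The omission of High-C is certain from the text. A stated prediction has no test, and the claim that High-C+ is the closest arm cannot be shown among the three arms.

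The circular selection is a well-supported but conditional inference. If YA values come from the selecting scans and the signal is the selecting contrast or one of its conditions, the direction of the bias is firm: YA upward on the contrast and the difficult condition, downward on the simple one. Its size rests on assumed activation and on the model. At YA n=20 the false rejection rate over all data sets in the parcel model runs from about 19% at 0.5 SD to 7% at 1.0 SD.

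The point concerns one additional comparison. It should be corrected because resemblance to younger brains is a stated purpose of scanning YA.

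**What to change.** 1. Run a four-group comparison (Low-C, High-C, High-C+, YA) and report each older arm minus YA with its 95% confidence interval. State that a non-significant difference will not be read as resemblance: an interval of about ±0.78 region-mean SD leaves room for large gaps. Signal is already to be extracted for all older adults, so the cost is wording and one more group.
2. Name, for each task, the signal entered in this comparison.
3. Choose regions independently of the YA values tested, by either of these:
   - Pre-specified atlas regions. These may be less task-specific: a set that is half inactive shows a true 0.30 SD gap as 0.15 SD.
   - Leave-one-subject-out selection in YA. When activation is weak, some folds may find no region, so the rule for such folds should be set in advance.
4. Reconcile the three YA sample sizes (18, 20, 25), since precision and bias both depend on them.

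The whole change is SAP wording and a small re-analysis, without new scans.

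### The younger-brain resemblance test omits older adults' pre-test values and the High-C arm, so alone it cannot show movement toward the younger pattern, and its old-young contrast is confounded with repeat scanning

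*Combined protocol and SAP*

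**What the plan says.** All references are to the combined protocol and SAP.

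- **Purpose of the YA group (Brief Summary).** "It will also help us determine whether older adults' brain activity following training resembles that of younger brains". The same section expects the two high-control arms to show heightened activation after the intervention, parallel to the baseline activity of younger brains.
- **Scans (Brief Summary).** MRI "will be conducted at baseline and at immediate post-training for older adults, and only once in younger adults". On training: "These younger adults will not undergo any training".
- **Data extracted (Data Analysis Plan, neuroimaging outcomes).** The "clusters from YA will be used to extract percent signal change for all older individuals (OA) at both assessments".
- **Test named for those regions (next sentence).** "A univariate ANOVA with 3 groups (post-test Low-C, post-test High-C+, and YA) will be conducted to evaluate whether the post-test activations in High-C+ older adults" lie closest to those of YA.
- **Prediction attached (the sentence after that).** Both High-C and High-C+ should come to mimic younger adults, with over-activation reduced relative to baseline.
- **Subsequent-memory task (Outcome Measures).** "Twenty minutes after the scan, the participant will undergo a recognition judgement task along with confidence ratings of their responses".

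Two other analyses bear on the point. Earlier in the neuroimaging section, a Training Arm x Assessment ANOVA with planned comparisons is specified for older adults' percent signal change. The Year 1 timeline plans a comparison of older adults' baseline fMRI with that of YA.

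**The concern.** The prediction is partly about movement: older adults should end nearer to the younger pattern than they began. The one test that brings YA in has no starting point. An arm that was already near YA at Assessment A looks the same in it as an arm that travelled there.

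Exposure is also unequal on the two sides of the old-young contrast. At Assessment B the older adults are doing the scanner tasks for the second time and have already met the recognition test that follows the memory scan. YA are scanned once. A familiarity effect would sit on one side only and could pass for resemblance.

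Finally, High-C is named in the prediction but absent from the test, so that half of the prediction has no stated comparison with YA.

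At stake is the claim that training makes older brains work more like younger ones. Episodic memory fMRI is listed as a primary outcome, so this is more than a side analysis.

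**Working it through.** **Inputs from the documents.** Older adults retained: 30 in three arms (Study Design); the ratio is not stated, so 10 per arm is assumed. YA: 18 (Brief Summary), 20 (Study Design) or 25 (Year 1 timeline); 18 is used here. Older adults have two scans, YA one.

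**Assumptions.** The documents give no alpha, SD, effect size or margin for this test, so there is no figure of its own to reproduce; the stated power figures concern the cognitive outcome. Assumed: two-sided 0.05, SD 1, an old-young gap of 0.8 or 0.5 SD, and pre-post correlation r of .3 to .7.

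**Step 1: what is extracted and what is used.**

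| Values in YA-derived regions | Extracted | In the YA test |
|---|---|---|
| Low-C, High-C+ at Assessment B | yes | yes |
| High-C at Assessment B | yes | no |
| All three arms at Assessment A | yes | no |
| YA, single scan | yes | yes |

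**Step 2: what the old-young contrast can show.** Its standard error is sqrt(1/10 + 1/18) = 0.394. A gap of 0.8 SD gives 0.8/0.394 = 2.03, almost exactly the critical t on 10 + 10 + 18 - 3 = 35 degrees of freedom (2.03). So about half of trials miss a gap that is fully present. Simulating the quoted ANOVA (20,000 runs, r = .5):

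| Scenario | High-C+ vs YA not significant | Low-C vs YA not significant | High-C+ vs Low-C significant | High-C+ nearer to YA than Low-C |
|---|---|---|---|---|
| Gap 0.8, nothing moves | 48.8% | 49.7% | 4.9% | 49.9% |
| Gap 0.5, nothing moves | 76.6% | 76.8% | 4.4% | 50.2% |
| Gap 0.8, retest closes half | 83.4% | 83.5% | 5.1% | 49.6% |
| Gap 0.8, retest closes all | 95.1% | 95.0% | 5.0% | 50.0% |
| Gap 0.8, High-C+ training closes all | 95.4% | 49.4% | 41.5% | 86.5% |

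The first result column barely separates the last two rows: retest and training look alike against YA. The High-C+ versus Low-C column does separate them, and stays near 5% whenever there is no training-specific effect.

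**Step 3: precision of the randomised contrast.** With 10 per arm the standard error is sqrt(2/10) = 0.447. A chance baseline difference above 0.5 SD in either direction occurs with probability 26%. This is already within the test's alpha; it is noise that a baseline covariate can remove. For a true difference of 0.8 SD:

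- Post-test only: 0.8/0.447 = 1.79, power 0.40.
- Baseline-adjusted: the standard error is multiplied by sqrt(1 - r^2), giving 0.427, 0.387 and 0.319 at r = .3, .5 and .7. The formula gives power 0.42, 0.50 and 0.66. Simulation that also pays for estimating the covariate slope gives about 0.41, 0.47 and 0.63.

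**Step 4: which measure to adjust.** In the same setting, baseline-adjusted *absolute* distance of each person from the YA mean has power of only about 0.13. Even a fully normalised group keeps individual spread around that mean, so absolute distance hides the shift. The signed signal does not have this problem.

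**The case against.** A reader might infer that the plan can show neither a shift in older adults nor its cause. The documents do not support that.

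- **Shift.** The Training Arm x Assessment ANOVA tests change among older adults. What it does not do is say whether the change is toward YA. It is described before the YA regions are introduced, and the prediction includes both increases and decreases, so direction alone does not settle approach. The Year 1 comparison is baseline only and is not linked to post-test.
- **Cause.** Low-C is a randomised arm with the same two scans, and it is in the quoted ANOVA. A retest effect common to both arms cancels in High-C+ versus Low-C at post-test, as it would in a comparison of change. Chance baseline differences reduce precision and do not bias the contrast. Allocation also balances frailty, age, education and gender, though not activation.

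Two further objections stand in part. The Brief Summary wording can be read as a question about the end state, which a post-test comparison answers in a limited way. And the size of any retest effect is unknown: the documents do not say whether scenes differ between scans or whether participants are told of the recognition test, and YA also have a mock scan. The unequal number of scans, however, is stated.

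**Conclusion.** The concern holds in limited form. The resemblance ANOVA omits older adults' pre-test values and High-C. Taken alone it cannot show movement toward YA, and its old-young contrast mixes age, training and repeat scanning. Under the assumptions above, apparent resemblance with no training effect arises in 49% of trials (gap 0.8 SD, no movement) to 95% (retest closes the gap), if resemblance is read as a non-significant difference. The plan does not define closest in any other way.

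The randomised comparison of High-C+ with Low-C remains valid and could be made more precise at no cost: power rises from 0.40 to about 0.41, 0.47 or 0.63 at r = .3, .5 or .7 for an assumed 0.8 SD effect. Because there is no untrained older group, no analysis here can separate training as such from retest; the design supports claims about high-control training relative to Low-C. The plan should be changed on this point, but its randomised comparisons are not undermined.

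**What to change.** 1. In the YA-derived regions, compare the signed percent signal change (the BOLD measure) at Assessment B between Low-C, High-C and High-C+, adjusted for the same region's Assessment A value. Do not use absolute distance from the YA mean.
2. Report each arm's signed gap to the YA mean at A and at B, with confidence intervals. Do not infer resemblance from a non-significant difference.
3. Attribute resemblance to high-control training only if the baseline-adjusted difference from Low-C is in the direction of the YA mean.
4. Keep post-test older adults versus YA as descriptive. State as a limitation that YA are scanned once while post-test older adults are on their second scan.
5. Reconcile the YA sample size (18, 20 or 25), since the gap intervals depend on it.

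Cost: analysis-plan wording only, because the values are already extracted at both assessments. The small downside is that a ranking of closest to YA at post-test no longer suffices for the claim.
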